2.5.2 Missing data

For data listings, the character date will always be used to present the date collected in the CRF.

Handling of computation of treatment duration if investigational medicinal product end of treatment date is missing

For the calculation of the treatment duration, the date of the last dose of IMP is equal to the date of last administration reported on the end-of-treatment case report form page. If this date is missing, the exposure duration should be left as missing.

The last dose intake should be clearly identified in the case report form and should not be approximated by the last returned package date.

Handling of multiple sclerosis medical history missing/partial dates

If the date of first MS diagnosis, first symptoms of MS or most recent relapse onset is incomplete, earliest possible day will be imputed for calculation, ie, unknown day will be set in 1st day of the month, and unknown month will be set in January. Unknown year will not be imputed.

Handling of medication missing/partial dates

For the purpose of determination whether the medication is prior or concomitantly, no imputation of medication start/end dates or times will be performed. If a medication date or time is missing or partially missing and it cannot be determined whether it was taken prior or concomitantly, it will be considered a prior, concomitant, and posttreatment medication.

For concomitant systemic corticosteroid used to identify invalid MRI scans (MRI should be done after a minimum of 14 days following the completion of a course of corticosteroid).

Below is the imputation rule:

If start day is missing, and start month and year are not missing:

Impute the start day using the first day of the month. Imputation flag is "D".

If start month is missing, and start year is not missing:

If end date is not missing/partial date, and the start year are the same as end date -5, then impute the start date using end date -5; if the year are earlier than end date -5, then impute the month and day using December 31. Imputation flag is "M". If the end date is also missing/partial date, this record will not be imputed and will not be used to identify invalid MRI scans.

If start year is missing:

If end date is not missing/partial date, impute the start date using end date -5. Imputation flag is "Y". If the end date is also missing/partial date, this record will not be imputed and will not be used to identify invalid MRI scans.

If end day is missing and end month and year are not missing:

If the end month and year are the same as start date +5, then impute the end date using start date +5; If the month and year are earlier than start date +5, then impute the day using the last day of the month; If the month and year are later than start date +5, then impute the day using the first day of the month. If this leads to a date after end of study follow up date, use the end of follow up date instead. Imputation flag is “D”.

If end month is missing and year is not missing:

If the end year are the same as start date +5, then impute the end date using start date +5; If the year are earlier than start date +5, then impute the month and day using December 31; If the year are later than start date +5, then impute the month and day using January 01. If this leads to a date after end of study follow up date, use the end of follow up date instead. Imputation flag is “M”.

If end year is missing:

Impute the end date using start date +5. If this leads to a date after end of study follow up date, use the end of follow up date instead. Imputation flag is “Y”.

A special note, if the systemic corticosteroid start day is missing and month and year are not missing, the rule of 5 days after the start would not apply for the initial imputation. Thus for these cases, after imputation of start date, the end date will be re-imputed by repeating the above rules. If the start month and/or year are missing, the end date will not be imputed and this record will not be used to identify invalid MRI scans.

The above data imputations will only be used to identify invalid MRI scans.

Handling of adverse events with missing or partial date/time of onset

Missing or partial adverse event onset dates and times will be imputed so that if the partial adverse event onset date/time information does not indicate that the adverse event started prior to treatment or after the treatment-emergent adverse event period, the adverse event will be classified as treatment-emergent. No imputation of adverse event end dates/times will be performed. These data imputations are for categorization purpose only and will not be used in listings. No imputation is planned for date/time of adverse event resolution.

Handling of adverse events when date and time of first investigational medicinal product administration is missing

When the date of the first IMP administration is missing, all adverse events that occurred on or after the day of randomization should be considered as treatment-emergent adverse events. The exposure duration should be kept as missing.

The last dose intake should be clearly identified in the case report form and should not be approximated by the last returned package date.

Handling of missing assessment of relationship of adverse events to investigational medicinal product

If the assessment of the relationship to IMP is missing, then the relationship to IMP has to be assumed and the adverse event considered as such in the frequency tables of possibly related adverse events, but no imputation should be done at the data level.

Handling of missing severity of adverse events

If the severity is missing for 1 of the treatment-emergent occurrences of an adverse event, the maximal severity on the remaining occurrences will be considered. If the severity is missing for all the occurrences, a “missing” category will be added in the summary table.

Handling of potentially clinically significant abnormalities

If a patient has a missing baseline he will be grouped in the category “normal/missing at baseline.”

For PCSAs with 2 conditions, one based on a change from baseline value of the double-blind period or a normal range and the other on a threshold value, with the first condition being missing, the PCSA will be based only on the second condition.

For a PCSA defined on a threshold and/or a normal range, this PCSA will be derived using this threshold if the normal range is missing; eg, for eosinophils the PCSA is >0.5 GIGA/L or $>ULN$ if $ULN \geq 0.5$ GIGA/L. When ULN is missing, the value 0.5 should be used.

Measurements flagged as invalid by the laboratory will not be summarized or taken into account in the computation of PCSA values.

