All critical or major deviations potentially impacting efficacy analyses, drug-dispensing irregularities, and other major or critical deviations will be summarized in tables giving numbers and percentages of deviations by treatment group. The critical or major deviations that related to the Covid-19, regardless of deviation categories, will be summarized by treatment group separately.

Kaplan-Meier estimates of the cumulative incidence of permanent IMP discontinuation for any reason will be provided for open-label period. Time to withdrawal will be defined as the number of days from the first open-label IMP intake date until the last IMP intake date for the open-label period. Patients who complete the open-label period will be censored at the date of end of the open-label period. A listing of patients, along with reasons for treatment discontinuation, will be provided with their relationship with Covid-19.

Additionally, the analysis populations for safety, efficacy, and pharmacokinetics (See [Section 2.3](#)) will be summarized in a table by number of patients on the enrolled population.

- Efficacy population
- Safety population
- Pharmacokinetics population.

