2.4.3.1 Extent of investigational medicinal product exposure

The extent of IMP exposure will be assessed by the duration of IMP exposure in the open-label period of the study.

Duration of open-label IMP exposure is defined as last dose date of teriflunomide - first dose date of teriflunomide +1 day in the open-label period, regardless of unplanned intermittent discontinuations (see [Section 2.5.2](#) for calculation in case of missing or incomplete data).

Duration of open-label IMP exposure will be summarized descriptively as a quantitative variable (number, mean, SD, median, minimum, and maximum). In addition, duration of treatment exposure will also be summarized categorically by numbers and percentages for each of the following categories and cumulatively according to these categories: >0 to ≤4 weeks, >4 to ≤12 weeks, >12 to ≤24 weeks, >24 to ≤48 weeks, >48 to ≤72 weeks, >72 to ≤96 weeks, >96 to ≤120 weeks, >120 to ≤144 weeks, >144 to ≤168 weeks, >168 to <192 weeks and ≥192 weeks. The number and percentage of patients by final open-label IMP dose and by dose at the end of PK

run-in of the open-label period will also be presented by each treatment group. A list of the patients who changed dose after the end of the PK run-in of the open-label period will be provided. The number and percentage of patients with each open-label IMP dose level by visit and with dose increase/decrease/unchanged by visit will also be presented by each treatment group if necessary. Cumulative exposure of the IMP taken in the double-blind and open-label treatment periods will be summarized with descriptive statistics from the first dose of IMP in the double-blind period to the last dose of IMP in the open-label period for each treatment group.

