If a patient has no clinical relapse after randomization in double-blind period and before treatment discontinuation/completion in the open-label period, the patient will be considered as free of relapse till the date of last IMP administration reported on the EOT page. If this date is missing, last dose date on the IMP administration page will be used.

Given that confirmation of relapse in the open-label period is based on objective neurological examinations, it is possible that a patient remained on treatment but did not perform any objective neurological examinations due to Covid-19 pandemic. If a patient reported suspected MS relapse and had no objective neurological examinations assessed afterwards due to the pandemic, the censor date will be the date of the last EDSS or FSS assessment.

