2.4.4.3 Analysis of additional efficacy endpoint

2.4.4.3.1 Annualized relapse rate

The annualized relapse rate (ARR) is defined as the number of confirmed clinical relapses occurred during the study per patient-year. It will be analyzed in open-label period only. A confirmed clinical relapse is defined as the appearance of a new clinical sign/symptom or clinical worsening of a previous sign/symptom (one that had been stable for at least 30 days) that persists for a minimum of 24 hours in the absence of fever. Each episode of relapse must be confirmed by the treating neurologist, based on the objective assessments by an independent evaluator (the examining neurologist) by documenting either of the following:

- A) A 1-point increase in at least two FS functions, or a 2-point increase in at least one FS function (excluding bowel/bladder and cerebral) from the previous clinically stable assessment, or;
- B) An increase of at least 0.5 point in EDSS score (unless EDSS=0, then an increase of at least 1.0 point is required) from the previous clinically stable assessment.

Relapses are collected on CRF page “MS relapse”. The objective confirmation, based on the protocol-defined criteria, is reported (Yes/No) in the CRF. Only confirmed clinical relapses will be used in the analysis.

A gross estimate of annualized relapse rate for a treatment group would be the total number of relapses for patients in the treatment group divided by the sum of standardized study durations for patients in the treatment group. Total number of confirmed clinical relapses and standardized study duration will be calculated for each patient.

- Total number of confirmed clinical relapses is defined as the number of confirmed clinical relapses with onset between enrollment date of the open-label period and treatment discontinuation/completion date (same as last dose IMP intake date).
- Standardized study duration (in year) will be calculated by (last dose IMP intake date - enrollment date of the open-label period + 1) / 365.25.

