3 INTERIM ANALYSIS

An interim analysis for open label CSR is planned at core DBL (ie, approximately 28 days after last patient last visit in the double-blind period of this study).

Only data collected up to the date of core DBL will be used for this interim analysis. Analysis results will be summarized in an interim CSR for this open-label period.

Summary of patient disposition, demographics and key baseline characteristics, concomitant medications, extent of IMP exposure and compliance will be provided, as described in [Section 2.2](#), [Section 2.4.1](#), [Section 2.4.2](#), and [Section 2.4.3](#), respectively, in the interim analysis report.

For efficacy endpoints, the interim analysis will be performed for the following efficacy endpoints in which details are provided in [Section 2.4.4](#).

- Time to first clinical relapse after randomization up to the end the open-label treatment period
- Time to first clinical relapse after enrollment of open-label period up to the end of open-label period
- Proportion of clinical relapse-free patients
- Magnetic resonance imaging (MRI) variables
 - Number of new/newly enlarged T2 lesions
 - Number of Gd-enhancing T1 lesions
 - Change in volume of T2 lesions
 - Change in volume of T1 hypointense lesions
 - Number of new hypointense T1 lesions
 - Proportion of patients free of new or enlarged MRI T2 lesions at 48, 96, 144 and 192 weeks
 - Percentage change in brain volume
- Cognitive outcome measured by the SDMT and Cognitive Battery Tests
- Annualized relapse rate
- Sustained disability progression (using EDSS).

Summary of teriflunomide PK levels at each visit will also be provided with descriptive statistics.

For safety endpoints, key safety results including TEAE, SAE, AESI, death, AEs leading to treatment discontinuation along with related laboratory values, vital signs, and Tanner scales, in which details are provided in [Section 2.4.4.4](#) will be provided in the interim analysis report. Long-term safety data reported in the double-blind and the open-label treatment period s will also be performed for this interim CSR.

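### Read literally, SAP 2.5.2 leaves exposure missing for every patient still on open-label drug at the interim analysis, and other interim outputs give those patients no end date

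*SAP*

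**What the plan says.** SAP 2.4.3.1 gives the exposure formula, "Duration of open-label IMP exposure is defined as last dose date of teriflunomide - first dose date of teriflunomide +1 day", and refers to 2.5.2 for missing data. SAP 2.5.2 fixes the source: "the date of the last dose of IMP is equal to the date of last administration reported on the end-of-treatment case report form page". If that page gives no date, the instruction is "If this date is missing, the exposure duration should be left as missing".

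SAP Section 3 states that "An interim analysis for open label CSR is planned at core DBL", about 28 days after the last double-blind visit. It asks for exposure and compliance by reference to 2.4.3 and annualized relapse rate (ARR) by reference to 2.4.4. It also says "Only data collected up to the date of core DBL will be used for this interim analysis", but gives no end date for patients still on treatment then.

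Three other interim outputs depend on a last dose:

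- **ARR (2.4.4.3.1):** "Standardized study duration (in year) will be calculated by (last dose IMP intake date" minus open-label enrolment date, plus one, over 365.25). The relapse count stops at the same date, which is equated with discontinuation or completion.
- **Discontinuation curve (2.2):** time runs to last intake. The only censoring rule is "Patients who complete the open-label period will be censored at the date of end of the open-label period".
- **Compliance (2.4.3.2):** the denominator is the doses planned in the treatment epoch, which 2.1.4 ends at the last open-label administration.

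For time to first relapse, 2.4.4.1 and 2.4.4.2.1 treat the same missing date differently: "If this date is missing, last dose date on the IMP administration page will be used".

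**The concern.** The missing-date rule suits a finished study, where an absent end-of-treatment date is an occasional data gap. At the core lock, an absent open-label end-of-treatment date is the normal state of any patient doing well on drug. Applied there, the rule selects the exposure summary on whether the patient has already stopped or was randomized early enough to finish.

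The interim open-label report would then set exposure for that subset beside adverse event percentages whose denominator is everyone in the safety population (2.4.5.1). The two could not be read together. For ARR, discontinuation and compliance, a programmer would have to invent an end date, and different choices give different patient sets and different person-time.

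**Working it through.** The plan prints no figure on this point, so the check is mainly a trace of the cross-references.

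1. Section 3 sends interim exposure to 2.4.3.
2. 2.4.3.1 needs a last dose date and sends missing dates to 2.5.2.
3. 2.5.2 accepts only the end-of-treatment page and otherwise leaves exposure missing.
4. SAP Appendix C defines end of treatment as the first visit following the final drug intake. A patient still taking open-label drug therefore has no open-label end-of-treatment date.
5. Nothing in Section 3 overrides step 3. Read literally, interim exposure is missing for every ongoing patient.

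The same trace for the other outputs ends differently. ARR, the discontinuation curve and compliance name no CRF page, and none adopts the leave-missing rule. For them the end date is undefined. In ARR the duration is first called a study duration, but the model offset is then called a treatment duration, which is the term 2.5.2 governs. If 2.5.2 is carried over, the offset is missing and ongoing patients drop out of the model. If the IMP administration page is used, they stay in.

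**How many patients might be ongoing (illustration).** From the documents: open label ends 192 weeks after each patient's randomization, the double-blind period lasts up to 96 weeks, and the lock is about 4 weeks after the last double-blind visit. Assumptions: uniform accrual over A weeks, no early stopping, and a last double-blind visit 96 weeks after the last randomization.

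- Lock = 96 + 4 = 100 weeks after the last randomization.
- A patient randomized x weeks before the last one is ongoing if x + 100 < 192, so x < 92.
- Ongoing share = min(1, 92/A).

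For the effect on mean exposure, assume also that everyone enters open label at week 96. Ongoing patients then have x + 4 weeks of open-label time, which totals 92²/2 + 4 × 92 = 4,600 per unit of accrual. Finished patients have 96 weeks each, which totals 96(A − 92). The mean over all patients is [4,600 + 96(A − 92)]/A.

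| Accrual A (weeks) | Ongoing share 92/A | Their share of open-label time | Mean exposure, all (weeks) | Mean, end-of-treatment page required |
|---|---|---|---|---|
| 130 | 71% | 56% | 63 | 96 |
| 156 | 59% | 43% | 69 | 96 |
| 208 | 44% | 29% | 76 | 96 |
| 270 | 34% | 21% | 80 | 96 |

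The documents do not state accrual length. The 270 weeks is the longest span they allow: from the original protocol date (30-May-2013) to amended protocol 3 (02-Aug-2018), which records enrolment as complete (1,890 days / 7). Early discontinuation would lower the ongoing shares. Early stoppers would also bring short exposures into the retained subset, so the direction of the error in mean exposure cannot be fixed from the documents.

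**The case against.** Most of the open-label efficacy plan already copes with ongoing patients. Both time-to-relapse analyses fall back to the IMP administration page. Freedom from new T2 lesions is censored at the last on-treatment MRI, and disability progression at the last on-treatment EDSS. Open-label efficacy is declared exploratory, safety is descriptive, and adverse event percentages are unaffected because their denominator is the safety population. All of this stands, and it limits how serious the point is.

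A reader might infer that the SAP excludes ongoing patients from ARR. It does not say so. 2.4.4.3.1 has its own formula, names no page and does not refer to 2.5.2. Exclusion is one possible implementation of a gap. A reader might also infer that every censoring rule in 2.4.4 should move to the cut-off. That would credit event-free MRI and EDSS time beyond the last assessment, which is worse than the present text.

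Timing is a fair objection too. Enrolment was complete by 02-Aug-2018, so adding 96 weeks and 28 days puts the core lock at about 02-Jul-2020 or earlier if visits ran to schedule. This SAP version cites protocol section 17.7, which was added on 10-Dec-2020. The interim may already have been run under SAP version 1 (approved 05-May-2019), which is not among the documents. The current text nevertheless still presents the interim as planned.

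For the final lock, leaving a missing duration missing can be defended as a deliberate convention. 2.5.2 wants the last dose clearly recorded and not approximated by the last returned package date. But the IMP administration page is a different source from a package return, and the same SAP accepts it for censoring.

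**Conclusion.** The point holds for exposure. The stated rule, followed through its cross-references, leaves interim exposure missing for every patient still on open-label drug. For ARR, the discontinuation curve and compliance the supportable statement is narrower: no end date is defined for those patients.

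At the final lock no one is still on open-label treatment, so the main problem disappears. What remains is that exposure is dropped for any patient without a last-dose date on the end-of-treatment page, such as some of those lost to follow-up. 2.4.4.1 and 2.4.4.2.1 resolve the same missing date from another page. The number affected is unknown and probably small.

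The interim size is an illustration only: 44% of patients ongoing with 208 weeks of accrual and 34% with 270, and higher shares with shorter accrual. It rests on uniform accrual, no early stopping and a lock about 100 weeks after the last randomization.

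This is a should-fix. The outputs are descriptive or exploratory, and the primary double-blind analysis is under a separate SAP. If the interim has already been run, only the fallback change matters for the final open-label report.

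**What to change.** Two sentences, one in 2.5.2 and one in Section 3:

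- **Patients on treatment at the cut-off.** End exposure, compliance, the ARR duration and the ARR relapse count at the data cut-off or at the last recorded dose before it, naming which. Censor these patients at the same date in the discontinuation curve in 2.2.
- **Any other missing end-of-treatment date.** Use the last dose date on the IMP administration page, as 2.4.4.1 and 2.4.4.2.1 already do.

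Leave the MRI and EDSS last-assessment censoring rules unchanged.

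The cost is those two sentences and one derivation change. No new data are needed, because the SAP already uses the IMP administration page as a source.

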2 STATISTICAL AND ANALYTICAL PROCEDURES

The data from the double-blind and the open label teriflunomide treatment periods will be the focus of the CSR of their respective period. The following statistical methods/considerations in this SAP relate to the analysis of the data from the open label period. The analysis of the data from the double-blind period was addressed in a separate SAP. The optional additional extension period will be reported separately.

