2.1.4 Safety endpoints

The safety analysis will be based on the reported adverse events and other safety information, such as clinical laboratory data, vital signs, ECG, etc.

Observation period

The observation period of the open-label period will be divided into 3 epochs:

- The **treatment** epoch is defined as the time from the first administration of the IMP in the open-label period to the last administration of the IMP in the open-label period.
- The **accelerated elimination** epoch is defined as the time from 1 day after the open-label treatment epoch up to 4 weeks (28 days) after the last administration of the IMP in the open-label period or up to the first administration in optional additional extension period, whichever occurs first.

The treatment-emergent adverse event (TEAE) period will include both treatment and accelerated elimination epochs.

- The **posttreatment** epoch is defined as the period of time starting from the day after the end of the treatment-emergent adverse event period up to the end of the open-label period (defined as the first dose of optional additional extension IMP for patients enter optional additional extension period, or the last protocol-planned visit, EOT +4W, in the open-label period or the resolution/stabilization of a followed-up AE for patients do not enter).

The on-study observation period is defined as the combination of TEAE period and posttreatment epoch.

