2.1.4.1 Adverse events variables

Adverse event observation period

- Treatment-emergent adverse events are adverse events that developed or worsened or became serious during the treatment-emergent adverse event period in the open-label period of the study.
- Posttreatment adverse events are adverse events that developed or worsened or became serious during the posttreatment period in the open-label period of the study.

All adverse events, including serious adverse events (SAEs) and adverse events of special interest (AESI) will be coded to a lower-level term (LLT), preferred term (PT), high-level term (HLT), high-level group term (HLGT), and associated primary system organ class (SOC) using the version of Medical Dictionary for Regulatory Activities (MedDRA) currently in effect at Sanofi at the time of database lock.

Record the occurrence of adverse events (including serious adverse events and AESI) from the time of signed informed consent until the end of the study.

AESIs include the following terms:

- Gastrointestinal disorders (Nausea and diarrhea)
- Hepatic disorders
- Pancreatic disorders
- Bone marrow disorders
- Infections and Infestations
 - A specific analysis of Covid-19 related adverse events will be performed, using the search terms described in Appendix D
- Hypersensitivity
- Severe skin reaction
- Malignancy
- Hypertension
- Cardiac Arrhythmias
- Pulmonary disorders (ILD)
- Embolic and Thrombotic
- Hemorrhage
- Peripheral neuropathy
- Convulsions
- Alopecia
- Psychiatric disorders

Additional AESIs may be identified through the ongoing studies. The complete list of AESIs and details of the grouping algorithm will be finalized prior to the Database Lock (DBL).

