2.3 ANALYSIS POPULATIONS

2.3.1 Enrolled population

The enrolled population is defined as patients who were randomized in the double-blind period and enrolled in open-label period analyzed according to the treatment group allocated by randomization in double-blind period (ie, placebo/teriflunomide versus teriflunomide/teriflunomide).

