2.4.5.1 Analyses of adverse events

Generalities

The primary focus of adverse event reporting will be on treatment-emergent adverse events (TEAEs) in the open-label period. Posttreatment adverse events will be described separately.

TEAEs will be further differentiated as "TEAEs during treatment epoch" and "TEAEs during accelerated elimination epoch". TEAEs during treatment epoch and TEAEs during accelerated elimination epoch will be analyzed separately and combined, as applicable.

If an adverse event date/time of onset (occurrence, worsening, or becoming serious) is incomplete, an imputation algorithm will be used to classify the adverse event as treatment-emergent, or posttreatment. The algorithm for imputing date/time of onset will be conservative and will classify an adverse event as treatment emergent unless there is definitive information to determine it is posttreatment. Details on classification of adverse events with missing or partial onset dates are provided in [Section 2.5.2](#).

Adverse event incidence tables will present by SOC, HLG, HLT, and PT, sorted in alphabetical order for each treatment group, the number (n) and percentage (%) of patients experiencing an adverse event. Multiple occurrences of the same event in the same patient will be counted only once in the tables within a treatment period. The denominator for computation of percentages is the safety population within each treatment group.

Sorting within tables ensures the same presentation for the set of all adverse events within the observation period (treatment-emergent, and posttreatment). For that purpose, the table of all treatment-emergent adverse events presented by SOC and PT sorted by the internationally agreed SOC order and decreasing frequency of PTs within SOCs will define the presentation order for all other tables unless otherwise specified. Sorting will be based on results for the overall treatment group.

Analysis of all treatment-emergent adverse events

The following treatment-emergent adverse event summaries will be generated for the safety population.

- Overview of treatment-emergent adverse events, summarizing number (%) of patients with any
 - Treatment-emergent adverse event
 - Serious treatment-emergent adverse event
 - Treatment-emergent adverse event leading to death
 - Treatment-emergent adverse event leading to permanent treatment discontinuation

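### When a first-dose date is missing, the open-label SAP anchors treatment-emergent adverse events to randomization, which pulls 8 to 96 weeks of double-blind events, including placebo events, into open-label teriflunomide tables

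*SAP*

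**What the plan says.** - **Scope.** SAP section 2 opens its methods with "The following statistical methods/considerations in this SAP relate to the analysis of the data from the open label period". The double-blind analysis has a separate SAP.
- **TEAE period.** In SAP 2.1.4 the treatment epoch is "defined as the time from the first administration of the IMP in the open-label period", and it closes with the last open-label dose. The TEAE period is that epoch plus the accelerated elimination epoch, which ends 28 days after the last open-label dose, or at the first optional-extension dose if that comes sooner.
- **TEAE definition.** SAP 2.1.4.1 defines treatment-emergent events as "adverse events that developed or worsened or became serious during the treatment-emergent adverse event period in the open-label period of the study".
- **Fallback rule.** SAP 2.5.2, for a missing first IMP date, says "all adverse events that occurred on or after the day of randomization should be considered as treatment-emergent adverse events". It does not say which period's first dose is meant, and it does not restrict the rule to events after open-label entry. The patient's exposure duration stays missing.
- **Where randomization sits.** SAP 2.3.1 describes the enrolled population as "patients who were randomized in the double-blind period and enrolled in open-label period".
- **Long-term safety analysis.** SAP 2.4.5.1 starts teriflunomide exposure at randomization for the teriflunomide group, but at the start of open label for the placebo group.

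**The concern.** The randomization anchor suits a double-blind analysis. Protocol 7.4 puts the first double-blind dose on the day of randomization or the day after, so an unknown first-dose date costs at most a day of misclassification. In an open-label SAP the same anchor reaches back over the patient's whole double-blind history.

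Two kinds of error follow for an affected patient. In the placebo/teriflunomide group, events that arose on placebo would be reported under open-label teriflunomide. In the teriflunomide/teriflunomide group, events would appear in the open-label tables although they may already be treatment-emergent in the double-blind report, whose TEAE period ends no later than open-label entry (Protocol 11.4.5). The error runs one way: it can add events to the open-label period but cannot remove any.

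**Working it through.** **Inputs**
- Total treatment from randomization to end of open label: 192 weeks (SAP 1.1).
- Maximum double-blind time: 96 weeks (SAP 1.1).
- Maximum open-label time: 184 weeks (SAP Appendix C, footnote r).
- TEAE tail after last dose: 4 weeks (SAP 2.1.4).
- Planned placebo patients: 55 (SAP 1.1).

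**Plan's own figure.** 192 − 8 = 184 weeks, which reproduces the stated maximum open-label duration. The shortest double-blind time before open label is therefore 8 weeks and the longest is 96.

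**Window length for a patient treated to Week 192**, with D double-blind weeks and no transition gap:
- By the TEAE definition: (192 − D) + 4.
- By the fallback rule: D + (192 − D) + 4 = 196.
- Double-blind share of the counted window: D/196.

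| D (weeks) | Window by definition | Window by fallback rule | Double-blind share |
|---|---|---|---|
| 8 | 188 | 196 | 8/196 = 4% |
| 48 | 148 | 196 | 48/196 = 24% |
| 96 | 100 | 196 | 96/196 = 49% |

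For a double-blind completer the window is 196/100 = 1.96 times its defined length. If such a patient stops open label at 24 weeks, it is 96 + 24 + 4 = 124 weeks instead of 28, and 96/124 = 77% of it is double-blind time.

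**Both readings of the trigger**
- *First open-label dose missing:* every double-blind event becomes an open-label TEAE.
- *First double-blind dose missing:* double-blind events are relabelled as open-label TEAEs even though the open-label start is known.

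The randomization anchor is wrong for the open-label tables either way.

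**Effect on a table.** The documents give no count of missing dates, so the number affected is an assumption. The lower denominator assumes that 20% of placebo patients do not enter open label: 55 × 0.80 = 44.
- No affected patient: no effect.
- One: 1/55 = 1.8 points, or 1/44 = 2.3 points.
- Five, as an illustrative upper case: 5/55 = 9.1 points, or 5/44 = 11.4 points.

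These shifts need patients who did not also report the same term during open label, because SAP 2.4.5.1 counts each patient once per event. The common-TEAE table uses a 2% cut-off in any group, so with 50 or fewer placebo/teriflunomide patients (1/50 = 2.0%) one misassigned patient could put a term into that table.

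**The case against.** **The trigger is rare.** Open-label drug is dispensed with an IVRS call at the transition visit (Protocol 1.3), dates of doses taken are recorded (Protocol 7.8), and PK sampling records the last intake (Protocol 9.11.1). The safety analysis is descriptive, without systematic testing. All of this stands, and it limits the size of the problem.

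**The wording may be harmless.** Elsewhere the SAP names the open-label dose when it means it, so the unqualified phrase could mean the first study dose. Section 2.1.4.1 could also be taken to override the rule. The ambiguity is real, but both readings misclassify double-blind events, and nothing in the SAP gives 2.1.4.1 precedence over this specific rule.

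**The rule is deliberately conservative.** Counting doubtful events as treatment-emergent is legitimate. It does not require reaching back across a different treatment.

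A reader might infer three stronger points that the documents do not support:
- *That SAP 2.4.5.1 has the same fault for incomplete onset dates.* It says its algorithm "will classify an adverse event as treatment emergent unless there is definitive information to determine it is posttreatment", but the same paragraph sends the reader to 2.5.2 for details. The partial-date rule there already excludes events shown to have begun before treatment. At most, the word treatment needs qualifying.
- *That double-blind events would fill the open-label discontinuation tables.* Protocol 5.1 opens the open-label period after a confirmed relapse, high MRI activity or completion of 96 weeks. A patient who permanently stopped double-blind drug for an adverse event has no ordinary route in.
- *That windows grow by 56% on average.* The planning placebo hazard of 0.4581 per year gives a mean of about 69.3 double-blind weeks, and 69.3/(192 − 69.3) = 56%. This is a ratio of means, not an average per patient. It omits the 28-day tail and treats relapse as the only reason to switch.

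**Conclusion.** The rule in SAP 2.5.2 is wrong as written for an open-label analysis. It contradicts SAP 2.1.4 and 2.1.4.1, and for placebo/teriflunomide patients also the long-term safety analysis in 2.4.5.1. Per affected patient it draws in 8 to 96 weeks of double-blind events, with a window of 196 instead of 100 weeks for a completer of both periods.

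It is a specification error with a likely small numerical effect. It acts only when a first-dose date is missing, the documents give no count, and few such cases are to be expected. The 1.8 to 2.3 points per affected placebo/teriflunomide patient rests on 55 to 44 patients entering open label and on the term being absent during open label. A reader might infer that open-label harm will be materially overstated; the documents do not support that.

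**What to change.** 1. In SAP 2.5.2, state that the rule concerns the first open-label IMP administration, and replace the randomization anchor with the date of enrollment in the open-label period (transition visit). The SAP already uses that enrollment date for the annualized relapse rate (2.4.4.3.1). The double-blind time counted then falls to about zero, or to the transition gap, which the flow chart recommends keeping under 2 weeks where possible.
2. For the long-term safety analysis, state the anchor by group: randomization for teriflunomide/teriflunomide, open-label enrollment for placebo/teriflunomide.
3. Optionally, say in the partial-onset-date rule of 2.5.2 that treatment there means the first open-label dose.

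The cost is a few sentences of SAP wording before database lock. No new data are needed.
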